The objective of the study is to evaluate the safety and efficacy of direct selective laser trabeculoplasty (DSLT) in normal tension glaucoma (NTG) in Asian patient populations. Studies have indicated that NTG has higher prevalence in Asian populations.¹⁰

Study Hypothesis:

It is hypothesized that the use of DSLT leads to the reduction of medication and IOP in Asian NTG patients.

Study Design

The study is a 12-month prospective, single arm, single center interventional study evaluating the safety and efficacy of DSLT in NTG patients.

Study Cohort

The study cohort will consist of approximately 40 Asian eyes with NTG of all severities on 1-3 glaucoma medications.

Study Sample Size & Justification

The sample size determination is based on the requirement that data from 30 eyes will provide sufficient information to evaluate the clinical performance of the treatment in this single-arm study. To account for an anticipated rate of screen failures and subject discontinuations of 20-25%, the total planned enrollment is up to 40 eyes

Anticipated Study Duration

The study duration will be approximately thirty months

Study Endpoints

Primary Endpoint:

- 12 months absolute washed out IOP (and IOP reduction) compared to washed out IOP at baseline

Secondary Endpoints:

- # of medication reduction at 11 months
- Proportion of patients that are medication free at 11 months
- Proportion of patients achieving $\geq 10\%$, 15% , and 20% IOP reduction at 12 months
- Rate of secondary surgical intervention (SSI) at 12 months

Exploratory Endpoints:

- Visual field and nerve stability as defined by change in visual field mean deviation and optical coherence tomography of the retinal nerve fiber layer (OCT RNFL) thickness at 12 months compared to baseline

Study Methodology

- **Screening/Baseline Visit 1:** Patients with NTG (glaucomatous optic neuropathy in patients with IOP measurements consistently lower than 21 mmHg) on 1-3 glaucoma medications will be screened, enrolled, and receive informed consent. If patients qualify to take part in this study, they will undergo:
 - Completed dilated fundus exam (DFE), Humphrey visual field 24-2 test (HVF 24-2), optical coherence tomography of the retinal nerve fiber layer (OCT RNFL), and central corneal thickness (CCT) within inclusion range
 - Patients using glaucoma medications will undergo washout period of 6 weeks
 - Washed out IOP must be ≤ 21 mmHg, both eyes are eligible to enroll

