 - Will restart patients back on meds (if any) for safety reasons (i.e. faster progression)
- **Visit 2:** Procedure Visit

- Patient will undergo DSLT (standard 1.8mJ, 120 shots, 360degrees)
- 1 drop tetracaine & brimonidine pre-procedure in treatment eye
- IOP check 5 mins and 1- 2 hours post-procedure
- As standard of care, IOP spikes and inflammation are treated at the discretion of the investigator
- One medication to be removed post-procedure
- Step down approach of medication removal for patient safety
- i.e. from 2 to 1 medication or 1 medication to no medication
- **Visit 3:** 1-month post-procedure (+/- 1 week)
 - IOP check
 - If IOP reduces $\geq 10\%$ from baseline screening medicated IOP then another medication is removed
 - Meds are reintroduced if IOP increases $>10\%$ from medicated baseline screening IOP
- **Visit 4 and 5:** 4 month and 8-month post- procedure (+/- 1 month)
 - As standard of practice, patients are seen every 3-4 months
 - IOP check
- **Visit 6:** 11 months- post-procedure (+/- 1month)
 - IOP check, not standard visit but prepare patient to do washout of medications (6 weeks)
- **Visit 7:** 12-13 months post-procedure
 - Washed-out IOP check
 - HVF 24-2, OCT, gonioscopy (check for PAS)
- Adverse event rates (IOP spike $>6\text{mmHg}$ and inflammation) and SSI will also be collected

Inclusion & Exclusion Criteria

Inclusion Criteria:

- Asian descent
- NTG diagnosis: glaucomatous optic neuropathy in patients with IOP measurements consistently lower than 21 mmHg
- Mean deviation (MD) of the visual field between 0 to -12dB
 - No significant central vision loss within 5 degrees within 5th percentile
- Age \geq 20 years
- NTG patients who are medically controlled on 1-3 medications and safe to wash out or IOP is still insufficient from medications and safe to washout
- Shaffer grade II or more on 3 of the 4 quadrants
- Central corneal thickness (CCT) 450–600 μ m
- All participants are able to provide written informed consent before participation

Exclusion Criteria:

- Angle closure glaucoma or narrow angle status post laser peripheral iridotomy (LPI), or any other open angle glaucoma excluding NTG
- History of SLT within last 2 years
- History intraocular surgery including refractive surgery, except for history of cataract surgery that has been greater than 1 year
- Patients anticipating cataract surgery during the study follow-up period
- Unable to have DSLT procedure due to pre-limbal findings

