- Any presence of relevant ocular diseases including retinal disease with no confirmed cure

Study Visit Assessments

	Screening/ Baseline	Visit 2 Procedure	Visit 3 1M F/U	Visit 4&5 4&8 M F/U	Visit 6 11M F/U	Visit 7 12.5M F/U
Demographics		X				
Consent						

Medication	X	X	X	X	X	X
CCT	X					
Gonio	X					X
IOP	X (washed out)	X	X	X	X	X (washed out)
DSLT		X				

STUDY PRODUCT INFORMATION

See Appendix for DFU

Adverse Event Assessment

Adverse event assessments will be per Principal Investigator discretion

Statistical Analysis

Descriptive statistics will be prepared for all study timepoints. For continuous variables, summaries will include the sample size, mean, standard deviation, median, minimum, and maximum. For categorical variables, summaries will report the number and percentage of eyes in each category. Analyses will include all eyes that complete the study.

A planned sub-analysis will be conducted on the subset of patients with a prior history of selective laser trabeculoplasty (SLT) to assess whether treatment outcomes differed from those without prior SLT.

Study Milestones & Timelines

Milestones	Estimated Timelines
Contracting	November 2025
IRB Approval	December 2025
First Patient, First Visit (FPFV) date or Data Collection start date	February 2026
Last Patient, Last Visit (LPLV) date or Data Analysis start date	January 2028
Final Clinical Study Report (CSR)	March 2028

Procedures for Recording and Reporting

All AEs will be documented on the Adverse Event case report form (CRF) and collected on a routine basis at monitoring visits. Procedure-related postoperative conditions that are normal consequences of ocular procedure and not clinically relevant will only be reported as adverse events at the discretion of the Sponsor-Investigator.

In addition, the Sponsor-Investigator must document all SAEs with details including the date of occurrence, severity, treatment (if applicable), outcome, and assessments of the seriousness and causality. All available information must be submitted to the study monitor immediately (ie, within 24 hours of the Sponsor-Investigator's knowledge of the event).

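### Safety rates are confined to eyes that complete the study, and the recording of inflammation is left to discretion, so the reported rates may be biased

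*Protocol*

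**What the plan says.** Under Study Objective, the protocol sets out to evaluate both safety and efficacy of DSLT. The visit list in Study Methodology closes by naming the safety outcomes: adverse event rates for an IOP spike above 6 mmHg "and inflammation) and SSI will also be collected". SSI at 12 months is also a secondary endpoint.

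Three later statements bear on how these rates are counted:

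- Adverse Event Assessment consists of one sentence: "Adverse event assessments will be per Principal Investigator discretion".
- Procedures for Recording and Reporting first commits to putting every AE on the case report form. It then adds an exception for some after-effects of the laser: "normal consequences of ocular procedure and not clinically relevant will only be reported as adverse events at the discretion of the Sponsor-Investigator".
- Statistical Analysis says "Analyses will include all eyes that complete the study". No separate safety set is described.

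For the procedure visit, Study Methodology requires "IOP check 5 mins and 1- 2 hours post-procedure". Completion of Study Records requires the results of protocol assessments to be kept for each subject. Neither the visit list nor the Study Visit Assessments table, as far as it can be read, contains an examination or grade for inflammation.

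**The concern.** There are two separate problems.

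The first is the analysis set. A safety rate describes what happens to eyes that receive the laser. Under the completer rule, an eye that is treated, has an event and then leaves is removed entirely, as is an eye that leaves without an event. The rate then describes eyes that stayed about a year, which is a different population if leaving is related to events. The same applies to SSI if an eye leaves after surgery.

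The second is ascertainment of inflammation. Mild inflammation after laser to the angle is easily classed as normal and not clinically relevant, so the discretion clauses can keep it off the AE form even though Study Methodology names it for collection. The commitment to document all AEs does not settle this, because it covers only what has already been judged an AE.

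The Background states that data on DSLT safety in NTG have not yet been reported in the peer-reviewed literature. These rates may therefore be read as first evidence.

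**Working it through.** **Inputs.** From Study Sample Size & Justification: 30 evaluable eyes, a combined 20-25% for screen failures and discontinuations (split not given), and up to 40 eyes enrolled. The protocol gives no expected event rate, so true rates of 10% and 20% are assumed for illustration.

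**1. The plan's own figure.** Enrolment = n/(1 − d). At d = 0.25, 30/0.75 = 40. At d = 0.20, 30/0.80 = 37.5, rounded up to 38. The stated figure of up to 40 is reproduced. The protocol states no safety rate or precision to reproduce.

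**2. Effect of the completer rule.** Let p be the true rate among treated eyes, L the overall loss and r the ratio of loss in eyes with an event to loss in eyes without.

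- Loss in eyes without an event: L/(p·r + 1 − p)
- Loss in eyes with an event: L_e = r·L/(p·r + 1 − p)
- Rate seen in completers: p(1 − L_e)/(1 − L)

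Example with p = 0.20, L = 0.25, r = 2: L_e = 2 × 0.25/1.2 = 0.4167, and the completer rate is 0.20 × 0.5833/0.75 = 15.6%.

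| Ratio of loss r | True rate 10% | True rate 20% |
|---|---|---|
| 0.5 | 11.6% | 23.0% |
| 1 | 10.0% | 20.0% |
| 2 | 7.3% | 15.6% |
| 3 | 5.0% | 12.4% |

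The bias has no fixed direction.

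**3. Bounds.** If all 40 eyes are treated and 10 leave, a true 4/40 (10%) can appear as anything from 0/30 (0%) to 4/30 (13.3%), and a true 8/40 (20%) as anything from 0/30 (0%) to 8/30 (26.7%). This is the widest case, because the 20-25% also covers screen failures before laser. If only 32 eyes are treated and 2 leave, a true 6/32 (18.8%) can appear as 4/30 (13.3%) to 6/30 (20.0%).

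**4. Effect of under-recording.** If a fraction f of events is recorded, whether or not the eye completes, the rate is multiplied by f. With r = 1 and a true 20%, f = 0.8 gives 16% and f = 0.5 gives 10%. This acts only downward. Each unrecorded event among 30 eyes moves the rate by 1/30 = 3.3 percentage points.

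**5. Which outcome can be recovered.**

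| | IOP spike | Inflammation |
|---|---|---|
| Numeric definition | Above 6 mmHg, reference reading not stated | None |
| Scheduled measurement | 5 minutes, 1-2 hours and later visits | None listed |
| Recoverable if not called an AE | Yes, once the reference is named | No mandated record |

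The reference matters because the protocol uses more than one baseline: the medicated screening IOP for the medication steps at Visit 3, and the washed-out IOP for the primary endpoint.

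**The case against.** The strongest reply is that the discretion clauses are narrower than they look. The second covers only conditions that are both normal consequences and not clinically relevant. It governs what is reported as an AE and does not cancel the separate commitment in Study Methodology to collect spikes, inflammation and SSI. The first may mean only the investigator's judgement of seriousness and causality, a sense in which the protocol itself uses the word assessment for serious events. There are also safeguards: AEs are collected at monitoring visits, all AEs go to the manufacturer within 24 hours irrespective of causality, and the records must cover other safety parameters.

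Much of this stands. It rules out saying that the protocol exempts both named outcomes from recording. The IOP spike can be derived from mandated, recorded readings whatever is called an AE. But the safeguards on AE reporting begin only once something has been judged an AE, and no required assessment produces an inflammation result. For inflammation the two commitments therefore pull against each other.

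It can also be said that a safety set could be defined in a statistical analysis plan that is not shown. That would answer an omission. Here the protocol states a rule for its analyses without exception, and the rule itself needs changing.

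**Conclusion.** The point holds in this form: treated eyes that do not complete the study are dropped from the spike, inflammation and SSI rates, which may bias those rates in either direction, and the discretion clauses can lower the inflammation count with no means of recovering it.

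For an assumed true rate of 20% and 25% loss, the completer rate runs from 23.0% to 12.4% as the ratio of loss goes from 0.5 to 3. Recording 80% or 50% of events, with equal loss, gives 16% or 10%. The true rates, loss ratios and recording fractions are all assumed. The 25% is an upper figure for loss after treatment, because it includes screen failures.

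A reader might infer that the safety rates are bound to be understated. The documents do not support that. The completer rule lowers a rate only if eyes with events leave more often, and nothing in the protocol says they do. Only the under-recording of inflammation has a fixed direction. A reader might also infer that an unmasked assessor is a stated feature. The protocol describes a single-arm design and a sponsor-investigator but says nothing about masking.

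**What to change.** 1. In Statistical Analysis, state that IOP spike, inflammation, other AE and SSI rates are reported over all eyes that received DSLT, whether or not they complete the study.
2. In Adverse Event Assessment and in Procedures for Recording and Reporting, state that the discretion clauses do not apply to the two named outcomes. Spikes are counted from the recorded IOP readings against a reference reading that the protocol names. Any observed inflammation is recorded with its grade, whether or not it is judged expected or clinically relevant.

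With every event recorded and all 40 eyes treated, the illustrative rates come back as 4/40 = 10% and 8/40 = 20%.

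The cost is a few sentences and one extra field on the form, and the reported rates may be somewhat higher. One limit remains: without a scheduled examination, the inflammation figure is a rate of inflammation seen, not of inflammation looked for, and the report should describe it so. Naming the grading scale and the visits at which inflammation is assessed would close that gap, at the price of some added visit work. The change should be made before data collection, because inflammation that was not recorded cannot be restored later.

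### The only analysis set is eyes that complete the study, so safety, SSI, interim IOP and 11-month medication data already observed in treated eyes that leave early are dropped

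*Protocol*

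**What the plan says.** The Statistical Analysis section of the protocol promises descriptive summaries at every timepoint. For categorical variables, "summaries will report the number and percentage of eyes in each category". It then fixes the population in one sentence: "Analyses will include all eyes that complete the study". The protocol does not define completion, and it names no treated set, safety set or per-visit set.

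The rule has to serve these parts of the protocol:

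- **Study Objective:** to "evaluate the safety and efficacy of direct selective laser trabeculoplasty (DSLT") in Asian patients with normal tension glaucoma, so safety is an aim alongside efficacy.
- **Primary endpoint:** "12 months absolute washed out IOP (and IOP reduction) compared to washed out IOP at baseline".
- **Secondary endpoints read at 11 months:** the number "of medication reduction at 11 months", and "Proportion of patients that are medication free at 11 months".
- **Secondary endpoint that accrues over follow-up:** "Rate of secondary surgical intervention (SSI) at 12 months".
- **Study Methodology:** IOP is checked at 5 minutes and 1 to 2 hours after the procedure, then at 1, 4, 8 and 11 months. A 6-week washout separates the 11-month visit (Visit 6) from the final washed-out visit (Visit 7). Rates of IOP spike and inflammation are collected, as is SSI.
- **Study Sample Size & Justification:** 30 eyes are wanted and up to 40 are enrolled. The reason given is "To account for an anticipated rate of screen failures and subject discontinuations of 20-25" percent.

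**The concern.** The rule makes the use of an early measurement depend on a later attendance. Whether an eye had a pressure spike within two hours of the laser is known that day. Under the rule it counts only if the eye is still in the study about a year later. The same holds for any SSI or inflammation before an eye leaves, for IOP at 1, 4 and 8 months, and for medication status at 11 months when the patient does not return after the washout.

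The study has one arm and a descriptive analysis, so no comparison exists in which such losses might balance out. The absolute rates are the findings. Conditioning them on completion changes the question from what happens to eyes treated with DSLT to what happened in eyes that stayed to the end. The two answers differ whenever leaving is related to outcome, and the protocol gives no ground for assuming that it is not. Reduction in medication is also half of the study hypothesis, so the 11-month endpoints are not a minor matter.

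**Working it through.** **1. The plan's own figure.** Target 30 eyes, loss 20–25%, enrolment up to 40 (Study Sample Size & Justification).

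- 30 / (1 − 0.25) = 40
- 30 / (1 − 0.20) = 37.5, rounded up to 38

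The 40 eyes reproduce at the upper loss rate.

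**2. How many treated eyes the rule can remove.** 40 × 0.20 = 8 and 40 × 0.25 = 10. Screen failures are never treated, and their share is not given, so treated losses lie between 0 and 10. With no screen failures and 10 losses, 10/40 = 25% of the procedure-day IOP data would be discarded. If every loss is a screen failure, the figure is 0%.

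**3. Which endpoints are touched**, reading completion as reaching Visit 7.

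| Endpoint | When observed | Effect of the rule |
|---|---|---|
| Washed-out IOP change; ≥10/15/20% reductions; visual field; OCT | Visit 7 | Essentially none: an eye with these data is a completer |
| Procedure-day IOP, adverse events | From Visit 2 | Early leavers removed |
| SSI | Throughout | Early leavers and their events removed |
| IOP at 1, 4, 8 months | Visits 3–5 | Early leavers removed |
| Medication reduction; medication-free | Visit 6 | Removed if the eye does not reach Visit 7 |

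**4. Illustrations.** The protocol gives no expected event rates. All event and visit counts below are assumptions, and each case takes 40 treated eyes with 30 completers, the ceiling of step 2.

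*Medication-free at 11 months.* Assume 36 eyes reach Visit 6, 15 are medication-free and 6 then leave. The observed rate is 15/36 = 41.7%. With k medication-free eyes among the 6 leavers, the rule reports (15 − k)/30:

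| k | Reported | Gap from 41.7% (points) |
|---|---|---|
| 0 | 50.0% | +8.3 |
| 1 | 46.7% | +5.0 |
| 2 | 43.3% | +1.7 |
| 3 | 40.0% | −1.7 |
| 4 | 36.7% | −5.0 |
| 5 | 33.3% | −8.3 |
| 6 | 30.0% | −11.7 |

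If leavers resemble completers (k of 2 or 3), the gap is small.

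*IOP spike on the procedure day.* Assume 4 of 40 treated eyes, or 10%. If 0, 1, 2, 3 or 4 of them complete, the rule reports 0/30 = 0%, 1/30 = 3.3%, 2/30 = 6.7%, 3/30 = 10.0% or 4/30 = 13.3%.

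*SSI.* Assume 3 events in 40 treated eyes, with j of those eyes completing. The rule reports j/30: 0%, 3.3%, 6.7% or 10.0% for j = 0 to 3. A Kaplan–Meier estimate that keeps all 3 events has 7 + j event-free leavers to censor.

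- If they leave after the last event: 3/40 = 7.5%.
- If they leave before the first event: 3/(33 − j), that is 3/33 = 9.1%, 3/32 = 9.4%, 3/31 = 9.7% and 3/30 = 10.0% for j = 0 to 3.

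That estimate therefore stays between 7.5% and 10.0%, while the completer rate can fall anywhere from 0% to 10.0%.

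**5. Precision.** If no event is seen, the one-sided exact 95% upper bound is 1 − 0.05^(1/n): 9.5% with 30 eyes and 7.2% with 40.

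**The case against.** The case on the other side has several parts.

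- **The sentence does not say only.** It says completers are included, and the promise of a sample size at each timepoint could fit a varying number of eyes. But no other set is named, so the exclusive reading is the natural one. If something else was meant, the same rewording settles it.
- **Completion is undefined.** This stands. The point about the 11-month endpoints rests on reading it as reaching Visit 7.
- **Analysis sets often belong in a statistical analysis plan, which may exist.** True of detail the protocol leaves open. Here the protocol states a rule, and a later plan with a treated set would depart from it.
- **Adverse events are recorded and reported anyway.** All of them go on the case report form and to the manufacturer, missing information must be explained in the final report, and the reason for leaving early is recorded. So individual events are not lost and attrition need not be hidden. None of this restores the observed data to a rate.
- **No bias is shown.** This also stands. The illustrations use assumed counts and the maximum treated loss. The 0% SSI case needs every eye with an SSI to leave, and nothing in the protocol withdraws an eye for that reason. If all such eyes stay, the completer rate is 10.0%, above the crude 7.5%.

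The reach is also limited: the primary endpoint survives.

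**Conclusion.** The concern holds. As written, the rule discards data already collected on treated eyes and gives adverse event, SSI, interim IOP and 11-month medication summaries that describe completers. Between 0 and 10 of 40 treated eyes are at stake, or 0% to 25%. The size and direction of the resulting bias cannot be derived from the protocol; it could be close to zero or, under the counts assumed above, around 10 percentage points either way for the medication-free rate (+8.3 to −11.7).

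The conclusion rests on two readings: that completers are the only set, and that completion means Visit 7. It does not extend to the primary washed-out IOP endpoint or the other Visit 7 measures, nor to the reporting of individual events. It should be fixed, but it does not undermine the study's main result.

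**What to change.** Replace the sentence on the analysis population with wording such as:

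> Adverse event and SSI summaries will include every eye that receives DSLT, showing length of follow-up and the number of eyes not followed to 12 months. Interim IOP and 11-month medication summaries will include every treated eye with data at that visit, with the number of missing values and the reasons. Visit 7 endpoints will include every treated eye with Visit 7 data, with the numbers treated and missing beside each result. Any analysis of completers will be labelled supportive, and completion will be defined.

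Two additions are optional: a time-to-event estimate for SSI that censors at the last visit, and a sensitivity analysis that counts missing responder or medication-free status as failure.

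The wording keeps the eye as the unit, as in the Statistical Analysis section. The Study Endpoints section words some proportions in terms of patients; that is a separate matter, and this change does not resolve it.

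The cost is a protocol text change. It needs no further data, visits or patients, since reasons for early discontinuation are already a required record. Denominators will differ between tables, and some rates may look less favourable; which ones cannot be known in advance.

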IRB PROTOCOL

Sponsor / Study Title: **The Effectiveness of DSLT in Asian Normal Tension Glaucoma Patients**

Protocol # **NTG_DSLT-001**

Investigator/ Sponsor **[name] and [name]**

[contact]**

Address: **[name]
[name]**

CONFIDENTIAL

This protocol contains confidential information. Further dissemination, distribution, or copying of this protocol or its contents is strictly prohibited.

Background:

Normal-tension glaucoma (NTG) is a form of open-angle glaucoma characterized by glaucomatous optic neuropathy in patients with intraocular pressure (IOP) measurements consistently lower than 21 mmHg¹ and has been shown to account for the majority of primary open-angle glaucoma (POAG) in the

population older than 40 years in Asian countries.² Lowering IOP remains the only proven intervention to delay progression, and even modest reductions can be beneficial in NTG.³ Selective laser trabeculoplasty (SLT) has demonstrated efficacy and safety in lowering IOP in primary open-angle glaucoma and ocular hypertension, but its role in NTG is recently emerging and less clearly established. Recent studies suggest that SLT can achieve clinically meaningful IOP reductions and decrease IOP variability in NTG patients, potentially slowing disease progression.^{4,5} SLT may also be an effective and safe treatment option for NTG, as either a first-line or second-line treatment.⁶ Studies looking at long term outcomes found that SLT achieved a ~22% IOP reduction with a 41% decrease in medication use, but absolute success without medications declined from 61% at 6 months to 11% at 24 months, with many eyes requiring retreatment.⁷

Direct selective laser trabeculoplasty (DSLT) is an emerging variant of SLT that delivers laser energy without the need for a contact lens—making it a non-contact and potentially more patient-friendly procedure. However, in the GLAURious study that compares the efficacy of DSLT and SLT, NTG patients were excluded from the study and data on DSLT's effectiveness or safety specifically in NTG patients has not yet been reported in the peer-reviewed literature.⁸

Unmet Medical Need:

DSLT offers potential procedural advantages in open angle glaucoma and ocular hypertension but lacks evidence specific to NTG in current studies.

Study Objective

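### An eye that has a secondary surgical intervention or repeat laser and attends Visit 7 brings its post-intervention IOP into the DSLT results and can count there as a responder

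*Protocol*

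**What the plan says.** The Statistical Analysis section fixes one population for all summaries: "Analyses will include all eyes that complete the study". It makes no exception for eyes that receive a further procedure.

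Under Study Endpoints, the primary endpoint is "12 months absolute washed out IOP (and IOP reduction) compared to washed out IOP at baseline". One secondary endpoint is "Proportion of patients achieving $\geq 10\%$, 15% , and 20% IOP reduction at 12 months". Two more concern medication at 11 months: the reduction in number of medications and the proportion free of medication. None of these is conditioned on the absence of an SSI. The SSI endpoint stands by itself: "Rate of secondary surgical intervention (SSI) at 12 months".

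Study Methodology says that SSI will be collected along with adverse events. It does not make SSI a reason to leave the study, a non-response, or a point after which IOP is set aside. It schedules a 6-week medication washout before the final IOP at Visit 7. The exclusion criteria cover "Patients anticipating cataract surgery during the study follow-up period", but nothing says how surgery that happens anyway is handled in the analysis. The study has a single arm.

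**The concern.** The primary and responder endpoints are meant to show what DSLT did to IOP. Washing out medication at both ends of the comparison serves that aim, because drug effect is removed before each measurement. A later IOP-lowering procedure cannot be washed out. If it lowers pressure, the Visit 7 value reflects DSLT plus that procedure, and in a single-arm study no comparison group offsets it.

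The same eye can then be a failure under the SSI endpoint and a responder under the IOP endpoints. The medication endpoints are open to the same problem when the intervention comes before Visit 6. This differs from the loss of non-completers: it arises from eyes that are kept. At stake is how the mean reduction and the responder proportions can be read, since they are the main efficacy results of a small descriptive study.

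**Working it through.** **The plan's own figure.** Study Sample Size & Justification gives 30 evaluable eyes, 20–25% screen failure and discontinuation, and enrolment of up to 40.
- 30 / (1 − 0.25) = 40.
- 30 / (1 − 0.20) = 37.5, rounded up to 38.

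The figure reproduces. I take n = 30 completing eyes below. The protocol gives no power, effect size or SD, and this point does not depend on them.

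**Following the rules for one eye.**
1. The eye receives DSLT, later has an SSI, and attends Visit 7.
2. No section makes the SSI a study exit, so on the natural reading the eye completes and is analysed.
3. Its washed-out IOP at Visit 7 is compared with its washed-out baseline. The washout has removed drug effect only.
4. If the reduction reaches 10, 15 or 20%, the eye is a responder at that level. If the SSI preceded Visit 6 and the eye is off medication then, it is also medication-free.
5. The SSI endpoint counts the same eye as an event.

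**Responder proportions.** Let k be the number of completing eyes with an SSI. The largest difference between counting them as observed and counting them as non-responders is k/30.

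| k | k/30 (percentage points) |
|---|---|
| 0 | 0 |
| 1 | 3.3 |
| 2 | 6.7 |
| 3 | 10.0 |
| 5 | 16.7 |

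This is an upper bound. An SSI eye that misses the threshold adds nothing.

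**Mean reduction, illustration only.** The protocol gives neither an SSI rate nor an expected effect. Assume a 15% mean reduction in eyes without SSI and an observed reduction s of 20–40% in eyes with SSI.
- As observed: mean = [(30 − k) × 15 + k × s] / 30.
- SSI eyes credited with no reduction: mean = (30 − k) × 15 / 30.

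| k | As observed, s = 20 to 40 | SSI eyes at 0% | SSI eyes set aside |
|---|---|---|---|
| 0 | 15.0% | 15.0% | 15.0% |
| 1 | 15.2–15.8% | 14.5% | 15.0% |
| 3 | 15.5–17.5% | 13.5% | 15.0% |
| 5 | 15.8–19.2% | 12.5% | 15.0% |

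For k = 3 and s = 40: (27 × 15 + 3 × 40) / 30 = 525 / 30 = 17.5%. At zero reduction: 405 / 30 = 13.5%. The spread shows that the handling rule matters once a few SSIs occur. It does not predict how many will.

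**The case against.** The strongest reply is that the quoted sentence settles which eyes are analysed, not which IOP value is used after an intervening procedure. That detail often sits in a SAP, and one may exist here. Study completion is not defined either, and the study records must give a reason for early discontinuation, so a site could record an SSI as a discontinuation. The plan has no hypothesis test or success threshold that a shift could flip, and the separate SSI rate keeps the failures visible.

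Part of this stands. The reading combines a population rule with unconditioned endpoints; no sentence says that post-surgery IOP is credited to DSLT. But the protocol is not silent. It fixes the analysis set and the endpoints, and a SAP that applied both literally would keep these eyes with their observed values. Recording an SSI as discontinuation would not help, because the completer rule would then drop the failure altogether. Reporting the SSI rate separately does not take the procedure's effect out of the IOP results.

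A reader might infer more than the text supports:
- **That many SSIs are expected.** Listing SSI as an endpoint does not forecast it. The Background remark "with many eyes requiring retreatment" concerns SLT results described out to 24 months and gives no rate. This study runs 12 months.
- **That the bias always favours DSLT, or that every SSI eye becomes a success elsewhere.** An eye may miss the threshold, still use medication at Visit 6, or have reached the threshold without the procedure. An SSI after Visit 6 cannot affect the medication endpoints.
- **That the mean is overstated by some known fraction.** Any such figure rests on assumed SSI counts, an assumed surgical effect and an assumed DSLT effect.
- **That zero reduction must be imputed in the primary mean.** If DSLT alone would have lowered IOP by an assumed 2 mmHg, imputing zero for 1 to 4 of 30 eyes understates the mean by k/30 × 2 = 0.07 to 0.27 mmHg.
- **That any intraocular surgery is a DSLT failure.** Cataract surgery may have nothing to do with pressure control.

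**Conclusion.** The point holds in a limited form. Followed literally, the analysis-set rule and the unconditioned endpoints let an eye that has an SSI or repeat laser trabeculoplasty, and then attends Visit 7, contribute its post-intervention IOP to the DSLT mean and possibly count as a responder. The effect is zero without SSI. Otherwise it is at most 3.3 percentage points per SSI eye in a responder proportion, with 30 completing eyes. The total cannot be stated, because SSI is neither defined nor given an expected rate, and the mean-reduction figures above are illustrations under stated assumptions.

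The conclusion assumes that an eye attending Visit 7 counts as completing. Whether repeat laser falls within SSI is also open; if it does not, such eyes would enter the IOP results without appearing in the SSI rate. The matter should be settled in advance, but it does not undermine the design.

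**What to change.** Add to Statistical Analysis:

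1. A definition of SSI, stating whether repeat laser trabeculoplasty is included.
2. An eye with an IOP-lowering SSI or repeat laser trabeculoplasty before Visit 7 counts as a non-responder at 10, 15 and 20%. It counts as not medication-free if the intervention precedes Visit 6.
3. For the primary mean IOP change, the as-observed result is shown beside a pre-specified summary that does not credit post-intervention IOP to DSLT. The value used should be named: for example, as a sensitivity analysis, the last washed-out value, the last pre-intervention value, or no reduction. On the current schedule the only washed-out IOP before Visit 7 is the baseline, so the first and third options coincide. A pre-intervention value from Visits 3 to 6 may be on medication, which should be stated when it is set against a washed-out baseline. Zero imputation need not be the primary analysis.
4. Surgery not done to lower IOP, such as cataract surgery, is flagged and examined in a sensitivity analysis, not called DSLT failure.

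SSI is already collected, and treatments during the study are already part of the study records, so the added data burden is at most the reason for and date of each procedure. The cost is a few sentences, one extra summary and a slightly less favourable responder rate if SSIs occur. The rule should be written before outcomes are seen.
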